## 7.5 Appropriateness of Selected Efficacy Endpoints

This study will be conducted to evaluate the efficacy of quizartinib in Japanese patients with FLT3-ITD positive relapsed or refractory AML. The reasons why the CRc was chosen as the primary efficacy endpoint are as follows: Prolonged OS has been reported in patients achieving CRc compared with patients failing to achieve CRc in the study in patients with relapsed or refractory AML, 15) and achievement of CRc in Japanese patients with relapsed or refractory AML allows them to undergo HSCT, which is expected to provide prolongation of OS.

#### 8. PHARMACOKINETIC/BIOMARKER ASSESSMENTS

The following items will be measured to evaluate the pharmacokinetics of quizartinib and quizartinib-related biomarkers.

## 8.1 Pharmacokinetic Endpoints

The pharmacokinetic parameters listed below will be calculated from the plasma concentrations of quizartinib and its active metabolite AC886 using a model independent approach.

Day 1 of Cycle 1: Cmax, Tmax, AUCtau

Day 15 of Cycle 1 and Day 1 of Cycle 2 (if the dose of quizartinib is increased on Day 16 of Cycle 1): Cmax,ss, Ctrough, Tmax,ss, AUCtau,ss

The details of the method of calculation of pharmacokinetic parameters are specified in

the Statistical Analysis Plan.

#### 8.1.1 Amount and Time Points of Blood Collection

Refer to "6.8 Pharmacokinetics."

#### 8.2 Biomarker Endpoints

- The presence or absence of mutations of the FLT3-ITD gene will be investigated using 2 mL of bone marrow liquid or 4 mL of peripheral blood collected after obtainment of informed consent, but before registration.
- The plasma inhibitory activity of quizartinib on phosphorylated FLT3 and c-Kit proteins will be measured using 2 mL of peripheral blood.

## 8.3 Anonymization, Storage, and Disposal of Specimens for Biomarker Testing

#### 8.3.1 Anonymization of Specimens

Prior to submission, the specimens will be anonymized with the subject identification code so that patient's personal information cannot be identified. Since the linking table between the subject identification code and their personal information will be strictly retained at the study center, not the sponsor, specimen collection agency, or biomarker assay facility can identify the patient's personal information. The sponsor can interlink biomarker study results to the subject identification code and the study data of the concerned patient.

## 8.3.2 Storage of Specimens

Considering the possibility that the relationship between the efficacy or safety of the study drug and biomarkers may be additionally measured, and the possibility that the items given in "6.9 FLT3-ITD Mutation Test" and "6.10 Biomarker Study" may be remeasured based on newly obtained knowledge, the submitted specimens will be stored at the biomarker assay facility for a maximum of 5 years after the end of the study. Biomarkers that may be additionally measured are point mutations and deletions in the tyrosine kinase domain of FLT3.

### 8.3.3 Disposal of Specimens

At the time of expiration of the specimen storage period, the biomarker assay facility will dispose of all the specimens as instructed by the sponsor.

If a patient withdraws consent for the study during the specimen storage period, the

specimens will be disposed of, depending on the location of the specimens at the time, according to the following procedure. If biomarker analysis has been performed at the biomarker assay facility before a patient's withdrawal of consent, the data will not be disposed of.

- 1) In cases where the specimens are temporarily stored at the study center:

  The investigators will identify the specimens of the patient and dispose of them.
- 2) In case the specimens are stored at the specimen collection agency or the assay facility:

The investigators will report the subject identification code of the pertinent patient to the sponsor. The sponsor will instruct the specimen collection agency or the assay facility to dispose of the specimens of the patient.

#### 9. SAFETY EVALUATION AND REPORTING

Safety endpoints are defined as AEs, laboratory data, body weight, ECOG PS, vital signs, 12-lead ECG, MUGA/echocardiography, and X-ray examination.

## 9.1 Adverse Event Collection and Reporting

All clinical AEs (for the definition, see "9.3.1 Definition of Adverse Events") that occur during the period from the day of the first dose of the study drug to the day of post-treatment observation will be recorded on the AE page of the CRF. SAEs that occur during the period from the day of informed consent to before the first dose of the study drug will also be recorded in the CRF.

Medical conditions (including laboratory values/vital signs that are out of range) that were diagnosed or known to exist prior to informed consent will be recorded as part of complications/medical history.

AEs and SAEs are to be reported according to the procedures in "9.4 Serious Adverse Events Reporting Procedure for Investigators."

All clinical laboratory results, vital signs, and 12-lead ECG results and findings should be appraised by the investigators to determine their clinical significance. Isolated abnormal laboratory results, vital sign findings, or ECG findings (ie, not part of a reported diagnosis) should be reported as AEs if they are symptomatic, lead to study drug discontinuation, dose reduction, require corrective treatment, or constitute an AE in the investigators' clinical judgment.

At each visit, the investigators will determine whether any AEs have occurred by evaluating the patient. AEs may be directly observed, reported spontaneously by the

patient or by questioning the patient at each study visit. Patients should be questioned in a general way, without asking about the occurrence of any specific symptoms. The investigators must assess all AEs to determine seriousness, severity, and causality, in accordance with the definitions in "9.3 Adverse Events." The investigator's assessment must be clearly documented in the site's source documentation.

Always report the diagnosis as the AE or SAE term. When a diagnosis is unavailable, report the primary sign or symptom as the AE or SAE term with additional details included in the narrative until the diagnosis becomes available. If the signs and symptoms are distinct and do not suggest a common diagnosis, report them as individual entries of AE or SAE.

For events that are serious due to hospitalization, the reason for hospitalization must be reported as the SAE (diagnosis or symptom requiring hospitalization). A procedure is not an AE or SAE, but the reason for the procedure may be an AE or SAE. Pre-planned (prior to signing the ICF) procedures or treatments requiring hospitalization for preexisting conditions that do not worsen in severity should not be reported as SAEs (refer to Section "9.3.2 Serious Adverse Events" for definitions).

For deaths, the underlying or immediate cause of death should always be reported as an SAE.

Any serious, untoward event that may occur subsequent to the reporting period that the investigators assesses as related to study drug should also be reported and managed as an SAE.

If any AE has occurred, the investigators will take appropriate actions, notify the sponsor as required, and continue follow-up until the patient recovers to the pre-event condition with resolution or relief of the AE as far as possible (even after the end of the specified observation period). However, even if the AE is not confirmed to have resolved or relieved, if it is judged that the patient's condition remains stable and the safety can be assured, the investigators will explain the matter to the patient, and the follow-up of the study will be completed (treatment of the relevant symptom will be continued).

#### 9.2 Safety Endpoints

Safety endpoints are defined as AEs, laboratory data, body weight, ECOG PS, vital signs, 12-lead ECG, MUGA/echocardiography, and X-ray examination.

#### 9.2.1 Combined Elevations of Aminotransferases and Bilirubin

Combined elevations of aminotransferases and bilirubin, either serious or nonserious and whether or not causally related, meeting the laboratory criteria of a potential Hy's Law case (ALT or AST  $\geq$  3 × upper limit of normal [ULN] with simultaneous total bilirubin  $\geq$  2 × ULN) should always be reported to the sponsor using a Serious Adverse Event Report (SAVER) form, with the investigators' assessment of seriousness, causality, and a detailed narrative. These events should be reported within 24 hours of investigators' awareness of the event.

If the patient discontinues study drug due to liver enzyme abnormalities, the patient will have additional clinical and laboratory evaluations as described in "5.7 Subject Withdrawal/Discontinuation" in order to determine the nature and severity of the potential liver injury.

#### 9.3 Adverse Events

### 9.3.1 Definition of Adverse Events

An AE is any untoward medical occurrence in a patient administered a pharmaceutical product and that does not necessarily have to have a causal relationship with this treatment. An AE can therefore be any unfavorable and unintended sign (including an abnormal laboratory finding, for example), symptom, or disease temporally associated with the use of a medicinal product, whether or not considered related to the medicinal product (International Conference on Harmonisation of Technical Requirements for Registration of Pharmaceuticals for Human Use [ICH] E2A Guideline. Clinical Safety Data Management: Definitions and Standards for Expedited Reporting, Oct 1994). It is the responsibility of investigators, based on their knowledge and experience, to determine those circumstances or abnormal laboratory findings which should be considered AEs.

The progression of the underlying disease (AML) will be handled as described below:

- Tumor progression will not be handled as an AE. However, tumor progression leading to the outcome of death during the AE collection period should be handled as an SAE (with the name and outcome of the event recorded as "disease progression" and "fatal," respectively).
- Tumor progression resulting in exacerbated signs or symptoms will be handled as an AE.

#### 9.3.2 Serious Adverse Events

An SAE is any untoward medical occurrence that at any dose:

- results in death,
- is life-threatening,
- requires inpatient hospitalization or prolongation of existing hospitalization for treatment,
- results in persistent or significant disability/incapacity,
- is a congenital anomaly or birth defect, or
- is an important medical event.

The term "life-threatening" in the definition of "serious" refers to an event in which the patient was at risk of death at the time of the event; it does not refer to an event which hypothetically might have caused death if it were more severe (ICH E2A Guideline. Clinical Safety Data Management: Definitions and Standards for Expedited Reporting, Oct 1994).

Medical and scientific judgment should be exercised in deciding whether expedited reporting is appropriate in other situations, such as important medical events that may not be immediately life-threatening or result in death or hospitalization but may jeopardize the patient or may require intervention to prevent one of the other outcomes listed in the definition above. Examples include allergic bronchospasm, convulsions, and blood dyscrasias or development of drug dependency or drug abuse.

#### Note:

- Procedures are not AEs or SAEs, but the reason for the procedure may be an AE or SAE.
- Pre-planned (prior to signing the ICF) procedures or treatments requiring
  hospitalizations for preexisting conditions that do not worsen in severity are not
  SAEs.

# 9.3.3 Severity Assessment

Severity of AEs will be assessed according to the Common Terminology Criteria for Adverse Events (CTCAE) v4.0 Japanese version. The severity of AEs not included in the CTCAE v4.0 Japanese version will be assessed according to the grades specified in Table 9.3-1.

Table 9.3-1 Evaluation of Severity of Adverse Events

Grade	Description
Grade 1	Mild; asymptomatic or mild symptoms; clinical or diagnostic observations only; intervention not indicated.
Grade 2	Moderate; minimal, local or noninvasive intervention indicated; limiting age appropriate instrumental activities of daily living (ADL).
Grade 3	Severe or medically significant but not immediately life threatening; hospitalization or prolongation of hospitalization indicated; disabling; limiting self care ADL.
Grade 4	Life threatening consequences; urgent intervention indicated.
Grade 5	Death related to AE.

Severity vs seriousness: Severity is used to describe the intensity of a specific event while the event itself, however, may be of relatively minor medical significance (such as severe headache). This is not the same as "seriousness," which is based on patient/event outcome at the time of the event.

# 9.3.4 Causality Assessment

The investigators should assess causal relationship between an AE and the study drug on the basis of his/her clinical judgment and the following definitions. The causality assessment must be made based on the available information and can be updated as new information becomes available.

#### Related:

- The AE follows a reasonable temporal sequence from study drug administration, and cannot be reasonably explained by the patient's clinical state or other factors (eg, disease under study, concurrent diseases, and concomitant medications).
- The AE follows a reasonable temporal sequence from study drug administration, and is a known reaction to the drug under study or its chemical group, or is predicted by known pharmacology.

#### • Not related:

 The AE does not follow a reasonable temporal sequence from study drug administration, or can be reasonably explained by the patient's clinical state or other factors (eg, disease under study, concurrent diseases, and concomitant medications).

# 9.3.5 Action Taken Regarding the Study Drug

- Dose not changed: No change in study drug dosage was made.
- Drug withdrawn: The study drug was permanently stopped.

- Dose reduced: The dosage of the study drug was reduced.
- Drug interrupted: The study drug was temporarily stopped.
- Dose increased: The dosage of the study drug was increased.
- Not applicable: patient died, treatment with the study drug had been completed prior to reaction/event, or reaction/event occurred prior to start of treatment.

#### 9.3.6 Other Action Taken for Event

- None.
  - No treatment was required.
- Medication required.
  - Prescription and/or over-the-counter (OTC) medication was required to treat the AE.
- Hospitalization or prolongation of hospitalization required.
  - Hospitalization was required or prolonged due to the AE, whether or not medication was required.
- Other.

#### 9.3.7 Adverse Event Outcome

- Recovered/Resolved
  - The patient fully recovered from the AE with no residual effect observed.
- Recovering/Resolving
  - The AE improved but has not fully resolved.
- Not recovered/Not resolved
  - The AE itself is still present and observable.
- Recovered/Resolved with sequelae/residual effect(s) present
  - The residual effects of the AE are still present and observable.
  - Include sequelae/residual effects.
- Fatal
  - Fatal should be used when death is a direct outcome of the AE.
- Unknown

#### 9.4 Serious Adverse Events Reporting-Procedure for Investigators

All AEs and SAEs will be reported in the CRF.

The following types of events should be reported by the investigator to the sponsor by telephone or on a SAVER form within 24 hours of awareness. The SAVER form for

reporting events to the sponsor should be sent via e-mail or fax.

- SAEs (refer to Section "9.3.2 Serious Adverse Events" for definition)
- Hepatic events meeting combination abnormalities (ALT or AST  $\geq$  3 × ULN with simultaneous total bilirubin  $\geq$  2 × ULN) (potential Hy's Law case), both serious and nonserious.

The investigator should report the details of each SAE in writing to the sponsor and the head of the study center. A written report to the head of the study center will be made in accordance with the procedures and format specified by the study center.

All events (serious and nonserious) must be reported with investigators' assessment of the event's seriousness, severity, and causality to the study drug. A detailed narrative summarizing the course of the event, including its evaluation, treatment, and outcome should be reported to the sponsor. Specific or estimated dates of event onset, treatment, and resolution should be included when available. Medical history, concomitant medications, and laboratory data that are relevant to the event should also be summarized in the narrative when available. For fatal events, the narrative should state whether an autopsy was or will be performed, and include the results if available. Source documents (including medical reports) will be retained at the study center and should not be submitted to the sponsor for SAE reporting purposes.

Urgent safety queries must be followed up and addressed promptly. Follow-up information and response to non-urgent safety queries should be combined for reporting to provide the most complete data possible within each follow-up.

The investigator must sign all completed SAVER forms, and then send them as attached documents to the appropriate e-mail address or fax them to the appropriate fax number. For the detailed reporting procedure, refer to the separately prepared procedural document.

The contact information for reporting SAEs is provided in "18.3 Sponsor's Safety Contacts" and the separately prepared procedural document. If there are any questions about reporting SAEs, the clinical monitor etc. should be contacted.

# 9.5 Notifying Regulatory Authorities, Investigators, and Institutional Review Board/Ethics Committee

If a serious adverse drug reaction occurs in other study centers enrolled in this study or other ongoing clinical studies of quizartinib, the sponsor should report to the

investigators, the institutional review board/ethics committee (IRB/EC), and the regulatory authorities.

# 9.6 Exposure In Utero during Clinical Studies

If it becomes known that a patient or a patient's partner has become pregnant during treatment with the study drug or within 6 months after discontinuation of treatment with the study drug, the investigators must notify the sponsor.

Although pregnancy is not technically an AE, all pregnancies must be followed to conclusion to determine their outcome. This information is important for both drug safety and public health concerns. It is the responsibility of the investigators to report any pregnancy in a female patient or a male patient's female partner using the form provided by the sponsor (Exposure in Utero Reporting Form). Please contact your study monitor to receive the Exposure in Utero Reporting Form upon learning of a pregnancy. The investigators should make every effort to follow the patient until completion of the pregnancy and complete the Exposure in Utero Reporting Form with complete pregnancy outcome information, including normal delivery and induced abortion. If the outcome of the pregnancy meets the criteria for immediate classification as an SAE (ie, post-partum complications, spontaneous or induced abortion, stillbirth, neonatal death, or congenital anomaly, including that in an aborted fetus), the investigators should follow the procedures for reporting SAEs outlined in Section 9.4.

# 9.7 Clinical Laboratory Evaluations

measurement results for the following items.

The following items will be measured. For clinical laboratory parameters, the reference range of the institution that performs the measurements will be used.

Information will be entered in the CRF on whether measured, date of measurement, and

- 1) Hematology test
  - Red blood cell count, MCV, MCH, MCHC, hemoglobin, hematocrit, white blood cell count, white blood cell differential count (neutrophils, basophils, eosinophils, lymphocytes, monocytes), platelet count, and PT-INR
- 2) Blood chemistry test

  Total protein, albumin, total bilirubin, direct bilirubin, AST, ALT, ALP, γ-GT, LDH,
  lipase, BUN, serum creatinine, creatine kinase, uric acid, glucose, electrolytes (K, Na,
  Cl, Ca, P, Mg), CRP, total cholesterol, LDL, HDL, and triglyceride
- 3) Urinalysis

Specific gravity, pH, occult blood, glucose, protein, bilirubin, and ketone bodies

#### 9.8 ECOG PS

The date of measurement and the results of investigators' assessment will be recorded in the CRF.

#### 9.9 Vital Signs

Blood pressure and pulse rate will be measured after the patient has rested in a recumbent position for 5 minutes or more.

Information will be entered in the CRF on whether or not measured, date of measurement, and measurement results for the following items.

Systolic blood pressure, diastolic blood pressure, pulse rate, body temperature, height, and body weight

#### 9.10 Electrocardiograms

#### 9.10.1 Measurement Method

ECG will be performed consecutively three times (triplicate ECGs) at intervals of 3 to 5 minutes after patients have remained at rest in the supine position for 10 minutes. The QTcF interval will be determined as the average of three measurements and used for safety evaluation and for making a decision on quizartinib dose increase on Day 16 of Cycle 1 and on Day 1 of Cycle 2 or later. The ECG results will be transferred to the Central ECG Reading Center (eResearch Technology, Inc. [ERT]). The investigators may check the ECGs without waiting for a central assessment if an urgent decision is required to assure the patient's safety at the study center.

If a foreseeable abnormal ECG finding is observed (eg, QTcF > 480 ms), the study center should contact the Central ECG Reading Center to request immediate assessment (within 24 hours), and determine the action to be taken for the patient (dose increase or reduction of the study drug etc.) based on the central assessment results. In this case, triplicate ECGs should be obtained again within 2 hours after the ECG measurement in which the above abnormal finding has been detected, and the results should be submitted to the Central ECG Reading Center.

The analysis results of the Central ECG Reading Center will be regarded as the final ECG data. All QT-related events will be decided using QTcF.

Additional ECG may be performed if the investigators consider it necessary. In such a case, the time of the ECG should be recorded. Triplicate ECGs should be obtained at all

the measurement time points, and the QTcF determined as the average of the three recordings will be used as the representative ECG data.

Whether to measure the ECG or not, date and time of measurement, and investigators' assessment results will be recorded in the CRF.

# 9.10.2 Measures Taken in Case of QTcF Prolongation

To reduce the risk of arrhythmia caused by quizartinib, laboratory monitoring should be performed to keep blood electrolytes (K+, Ca++, and Mg++) within the institutional reference ranges, and further to ensure K+ levels of 4.0 mEq/L or more as far as possible. If Grade 2 or more severe QTcF prolongation occurs, treatment should be given according to the following procedure. In patients for whom treatment with quizartinib is interrupted or the dose of quizartinib is reduced in association with Grade 2 or more severe QTcF prolongation, 12-lead ECG should be performed at any subsequent appropriate timing to carefully confirm whether QTcF prolongation has recovered or not.

# Grade 2 (QTcF: 481 ms to 500 ms)

- Measure electrolyte levels (K+, Ca++, and Mg++) and supply the electrolytes to ensure recovery to the institutional reference ranges.
- Check concomitant drugs, and discontinue drugs that are known to prolong QTcF, as necessary.
- Reduce the dose of quizartinib by one level. It is not necessary to interrupt treatment.
- The dose may be increased to the dose before dose reduction if QTcF prolongation recovers to Grade 1 or less severe after treatment at the reduced dose for at least 28 days. However, whether prolongation of QT interval occurs or not should be confirmed carefully for the first cycle (28 days) after the dose increase.

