## 5.4 Dose Interruptions and Reductions

If any of the criteria in Section 5.4.1 to Section 5.4.4 apply, treatment with quizartinib will be interrupted or the dose of quizartinib will be reduced. The dose of quizartinib will be reduced by one level at a time according to Table 5.4-1. If quizartinib is administered at a dose of 20 mg/day, a further dose reduction is not allowed.

Table 5.4-1 Method of Dose Reduction of Quizartinib

Dose	One level Reduced Dose
60 mg/day	30 mg/day
30 mg/day	20 mg/day
20 mg/day	No dose reduction

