## **5.4.1 QTcF Prolongation**

In case of QTcF prolongation, the dose will be reduced in the following manner.

Table 5.4-2 Criteria for Dose Interruption and Reduction When QTcF Prolongation Occurs during Treatment with Quizartinib at 30 mg/day or 60 mg/day

CTCAE Grade	Method of Dose Reduction		
Grade 2	
 
Reduce the dose by one level. It is not necessary to interrupt treatment.
 
The dose may be increased to the dose before dose reduction if QTcF prolongation recovers to Grade 1 or less severe after treatment at the reduced dose for at least 28 days.
 
		
Grade 3	
 
Interrupt quizartinib treatment for a maximum of 14 days.
 
Resume quizartinib treatment at a one level reduced dose, relative to the dose immediately before the interruption, if the increase in QTcF interval from baseline is 30 ms or shorter or the QTcF interval recovers to 450 ms or shorter within 14 days after the onset.
 
Do not increase the dose after resumption of quizartinib treatment.
 
		
Grade 4	Discontinue quizartinib treatment.		

For the treatment of QTcF prolongation, "9.10.2 Measures Taken in Case of QTcF Prolongation" should be followed.

Table 5.4-3 Criteria for Dose Interruption and Reduction When QTcF Prolongation Occurs during Treatment with Quizartinib at 20 mg/day

CTCAE Grade	Method of Dose Reduction	
Grade 2	
 
Interrupt quizartinib treatment for a maximum of 14 days.
 
Resume quizartinib treatment at a dose of 20 mg/day if QTcF prolongation recovers to Grade 1 or less severe.
 
	
Grade 3	
 
[If strong CYP3A4 inhibitors are concomitantly used]
 
Interrupt quizartinib treatment for a maximum of 14 days.
 
Resume quizartinib treatment at a dose of 20 mg/day if the increase in QTcF interval from baseline is 30 ms or shorter or the QTcF interval recovers to 450 ms or shorter within 14 days after the onset, and the concomitant use of strong CYP3A4 inhibitors is discontinued.
 
Do not increase the dose after resumption of quizartinib treatment.
 
[If strong CYP3A4 inhibitors are not concomitantly used]
 
Discontinue quizartinib treatment.
 
	
Grade 4	Discontinue quizartinib treatment.	

For the treatment of QTcF prolongation, "9.10.2 Measures Taken in Case of QTcF Prolongation" should be followed.

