#### Grade 3 (QTcF $\geq$ 501 ms)

- Measure electrolyte levels (K+, Ca++, and Mg++) and supply the electrolytes to ensure recovery to the institutional reference ranges.
- Check concomitant drugs, and discontinue drugs that are known to prolong the QT interval, as necessary.
- Interrupt treatment with quizartinib for a maximum of 14 days. Resume treatment with quizartinib at a one-level reduced dose, relative to the dose immediately before the interruption, if the increase in QTcF interval from baseline is 30 ms or shorter or

the QTcF interval recovers to 450 ms or shorter within 14 days after the onset. If Grade 3 QTcF prolongation occurs, subsequent dose increase is not allowed.

Grade 4 (increased QTcF to 501 ms or longer or a 60 ms or longer change in QTcF from baseline associated with any signs or symptoms of TdP, polymorphic ventricular tachycardia, or any other serious arrhythmia)

- Measure electrolyte levels (K+, Ca++, and Mg++) and supply the electrolytes to ensure recovery to the institutional reference ranges.
- Check concomitant drugs, and discontinue drugs that are known to prolong the QT interval, as necessary.
- Discontinue treatment with quizartinib.

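### Section 9.10.2 applies the 30/60 mg/day QTcF rules to every patient, so at 20 mg/day its Grade 2 order contradicts Table 5.4-3 and its Grade 3 restart cannot be carried out

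*Combined protocol and SAP*

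**What the plan says.** The protocol gives QTcF dosing rules in two places.

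**Section 5.4.1** separates them by dose. Table 5.4-2 covers 30 and 60 mg/day: at Grade 2, go down one level without a break; at Grade 3, hold for up to 14 days and restart one level lower. Table 5.4-3 covers 20 mg/day. At Grade 2 it requires a hold of up to 14 days, and then "Resume quizartinib treatment at a dose of 20 mg/day if QTcF prolongation recovers to Grade 1 or less severe". At Grade 3 it depends on co-medication. With a strong CYP3A4 inhibitor, drug is held and may restart at 20 mg/day only if QTcF recovers and "the concomitant use of strong CYP3A4 inhibitors is discontinued". The other branch, headed "If strong CYP3A4 inhibitors are not concomitantly used", is permanent discontinuation. Section 5.4 also states: "If quizartinib is administered at a dose of 20 mg/day, a further dose reduction is not allowed".

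**Section 9.10.2** does not separate by dose. Its scope sentence reads "If Grade 2 or more severe QTcF prolongation occurs, treatment should be given according to the following procedure". Its Grade 2 text is "Reduce the dose of quizartinib by one level. It is not necessary to interrupt treatment", and its Grade 3 text is "Resume treatment with quizartinib at a one-level reduced dose, relative to the dose immediately before the interruption", subject to QTcF recovery within 14 days. It does not mention 20 mg/day and does not refer back to 5.4.1. The note under each table, including the one for 20 mg/day, sends sites to this section: "For the treatment of QTcF prolongation, '9.10.2 Measures Taken in Case of QTcF Prolongation' should be followed".

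**The concern.** A dose of 20 mg/day is a planned part of the regimen. It is the starting dose with a strong CYP3A4 inhibitor (Section 5.2.4.1). It is also the step below 30 mg/day, reached after QTcF prolongation at 30 mg/day (Table 5.4-2) or when a strong inhibitor is added (Section 5.4.4). Some of the patients on it will therefore already have shown QTcF prolongation.

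For these patients the two sections give different orders on the drug's main cardiac risk. The Grade 2 case matters most. The one-level reduction in 9.10.2 cannot be done, so the only part of its dosing order that can still be followed is that a break is not needed. At stake are patient safety and uniform conduct across sites. The statistical design is not affected, and no effect on the CRc rate has been established.

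**Working it through.** **Rules side by side for a patient on 20 mg/day**

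| QTcF grade | Table 5.4-3 | Section 9.10.2 | Result |
|---|---|---|---|
| 2 | Hold up to 14 days; restart at 20 mg/day on recovery to Grade 1 or less | Reduce one level; break not needed | Conflict; the reduction is barred by Section 5.4 and Table 5.4-1 |
| 3, strong inhibitor | Hold; restart at 20 mg/day after recovery and with the inhibitor stopped | Hold; restart one level lower | Restart dose does not exist |
| 3, no strong inhibitor | Discontinue | Hold; restart one level lower | Restart dose does not exist |
| 4 | Discontinue | Discontinue | No conflict |

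At 30 and 60 mg/day, 9.10.2 agrees with Table 5.4-2.

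Read literally at Grade 3, 9.10.2 keeps the drug on hold until item 6 of Section 5.7.1 (interruption beyond 14 days) ends treatment. No exposure is added. A patient on an inhibitor could lose a restart that the table allows.

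**What a hold changes**

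Inputs: half-life about 3 days (Section 1.2.1.2.5) and a linear relationship between QTc prolongation and plasma AC220 (Section 3.2.2). The fraction of the steady-state level left after *d* days off drug is 2^(−d/3):

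- 1 day: 2^(−1/3) = 0.79
- 3 days: 2^(−3/3) = 0.50
- 7 days: 2^(−7/3) = 0.20
- 14 days: 2^(−14/3) = 0.04

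Continued dosing leaves 1.00. If a strong inhibitor doubled the half-life to 6 days (an assumption; the documents give no such figure), 7 days would leave 2^(−7/6) = 0.45 and 14 days 2^(−14/6) = 0.20.

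**How many patients**

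The documents give neither the share of patients at 20 mg/day nor QTcF rates at that dose. Two assumptions are needed:

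- Between 10% and 50% of 41 patients, or about 4 to 20, are at 20 mg/day at some time. Section 5.6.2.2, which says strong inhibitors should be avoided, pushes this down; the step-downs in Sections 5.4.1 and 5.4.4 push it up.
- The rates in Table 1.2-1 for 30 mg/day (N = 38) and 60 mg/day (N = 36) stand in for 20 mg/day. Counts are inferred from the rounded percentages.

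*Grade 2* (5% and 14%, so 2/38 and 5/36):
- Range: 4 × 0.05 = 0.2 to 20 × 0.14 = 2.8 patients.
- Pooled: 7/74 = 9.5%, Clopper-Pearson 95% CI 3.9% to 18.5%. The upper limit on 20 patients gives 20 × 0.185 = 3.7.
- Middle of the range: 12 × 0.095 = 1.1.

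*Grade 3* (5% and 3%, so 2/38 and 1/36):
- Range: 4 × 0.03 = 0.1 to 20 × 0.05 = 1.0 patients.
- Pooled: 3/74 = 4.1%, 95% CI 0.8% to 11.4%. The upper limit on 20 patients gives 20 × 0.114 = 2.3.

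The Japanese Phase 1 study (Section 1.2.1.2.4) saw no Grade 3 or worse prolongation in 9 subjects. The upper 95% limit for 0/9 is 1 − 0.025^(1/9) = 33.6%, so it does not narrow the range.

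**The case against.** The best defence is that the protocol already divides the labour. Section 5.2.4.1 assigns dose reduction to Section 5.4 and treatment of the prolongation to 9.10.2, and Section 5.4 makes its own criteria binding. On that reading 9.10.2 is about electrolytes, co-medication and ECGs, and the table written for 20 mg/day is the more specific rule. Saying a break is not necessary also does not forbid one. And Section 9.10.1 asks for repeat ECGs and a rapid central reading once QTcF exceeds 480 ms.

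Much of this is fair, and many sites would reach the right answer. It does not remove the contradiction: 9.10.2 issues dosing orders of its own, no sentence gives the tables priority, and the note under Table 5.4-3 directs sites to 9.10.2. The extra ECGs confirm the grade but do not say which dosing rule to follow.

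Three further points limit the size of the problem and stand:

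- Fourteen days is a maximum. A short hold leaves much of the drug on board, and exposure returns to the 20 mg/day level after restart. The 4% figure is the most favourable case for the hold.
- Table 5.4-2 itself moves a patient with Grade 2 prolongation from 30 to 20 mg/day without a break, so the protocol accepts some 20 mg/day dosing during a Grade 2 event.
- The patient numbers count events, not harm. Harm also needs a site to follow 9.10.2 rather than the table, and the documents give no basis for that probability.

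**Conclusion.** The concern holds. Section 9.10.2 is wrong as written for patients on 20 mg/day: it contradicts Table 5.4-3 at Grade 2 and names a non-existent restart dose at Grade 3. The safety issue is at Grade 2, where drug could be continued when the table requires a hold. The Grade 3 issue is inconsistent conduct only.

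The reach is small: probably no more than three patients with a Grade 2 event at 20 mg/day, and one or two at Grade 3. This rests on the assumed 10% to 50% share at 20 mg/day and on rates borrowed from higher doses. The textual conflict rests on neither. The correction should be made because it concerns a safety instruction and needs only wording.

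**What to change.** In Section 9.10.2, delete the dose-action bullets under Grade 2 and Grade 3 and put in their place: *Follow Table 5.4-2 (30 or 60 mg/day) or Table 5.4-3 (20 mg/day).* Keep the text on electrolytes, concomitant drugs and ECG monitoring, including the close QT monitoring after a dose is raised again. The Grade 4 text can stay.

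The cost is a wording amendment. It needs no extra patients, visits or procedures, and it leaves the dosing rules of Section 5.4.1 unchanged.
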